7.5 Pharmacokinetics

PK parameters are not evaluated in this study.

8 Statistical Considerations

8.1 Sample Size Determination

A total of 30 patients will enter the 3-treatment crossover study. The study will have 80% power to detect a treatment difference on the primary endpoint at a two-sided 0.05 significance level, if the true difference between treatments on HB is at least -3.7 %min/h. This assumes that the within-subject standard deviation is 9 and a discontinuation rate of less than 20%.

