4.1 Overall Design

Study APC-004 is a randomized, double blind, placebo-controlled, 3-period, single-dose crossover study to evaluate the safety and efficacy of two different dose combinations of AD-109 in patients with mild- to moderate OSA. Participants will undergo initial pre-screening to

determine potential study eligibility. Patients selected for further screening should either have a previous history of OSA of a severity consistent with enrollment criteria or be at high risk (e.g. as assessed by STOP-Bang Questionnaire score). Only patients who meet all non-PSG enrollment criteria at Visit 1 are eligible for a screening PSG.

Patients who meet all enrollment criteria will be randomized to receive the following experimental treatments, one treatment on each of 3 PSG night, separated by at least a one week washout period:

- Atomoxetine 75 mg + R-oxybutynin 2.5 mg (i.e. 75/2.5)
- Atomoxetine 37.5 mg + R-oxybutynin 2.5 mg (i.e. 37.5/2.5)
- Placebo

[figure not shown]
Dosing of the study treatment will occur immediately prior to lights out. The morning following each PSG exam in the crossover period the DSST, KSS, and sleep quality VAS will be administered approximately 1 hour after awakening.

Each PSG night is followed by a 1-week washout period. AE/SAE information is recorded at each study visit and by telephone contact with participants during each washout period.

Primary efficacy and safety endpoints will compare the 75/2.5 and 37.5/2.5 doses to each other and to placebo. AE/SAE information is recorded at each study visit and at the End of Study Evaluation.

Participants who withdraw from the study will not be replaced. No subsequent open-label extension is planned following the study.

Figure 1: Overview of Study Design

PSG = polysomnography.

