2.2. Endpoints

2.2.1. Primary Endpoint

The primary efficacy endpoint is change in \log_{10} of Hypoxic Burden (HB) 4% plus one (scored in reference to AHI[4%]), 75/2.5 dose vs. placebo

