9. SAMPLE SIZE AND POWER CALCULATIONS

A total of 30 patients will enter the 3-treatment crossover study. The study will have 80% power to detect a treatment difference on the primary endpoint at a two-sided 0.05 significance level, if the true difference between treatments on HB is at least -3.7 % min/h. This assumes that the within-participant standard deviation is 9 and a discontinuation rate of less than 20%.

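### The stated 80% power does not follow from the stated inputs: a within-subject SD of 9 and a difference of 3.7 %min/h give about 28–35% with 24–30 participants, on a scale that is not the SAP's primary endpoint

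*Protocol*

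**What the plan says.** Protocol 8.1 gives every input needed to check its claim. On size: "A total of 30 patients will enter the 3-treatment crossover study". On power: "The study will have 80% power to detect a treatment difference on the primary endpoint at a two-sided 0.05 significance level". The effect size behind that claim is a difference of 3.7 %min/h in untransformed HB. On variability and loss: "This assumes that the within-subject standard deviation is 9 and a discontinuation rate of less than 20" per cent. Protocol 4.1 adds: "Participants who withdraw from the study will not be replaced". At the 20% limit, 30 participants therefore become 24.

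SAP section 9 carries the same statement, with the wording "if the true difference between treatments on HB is at least -3.7 % min/h. This assumes that the within-participant standard deviation is 9". Neither document gives a formula, a within-participant correlation or a source for the 9.

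The documents differ on the scale of the endpoint. Protocol section 3 defines the primary endpoint as change in HB 4% with no transformation. SAP 2.2.1 defines it as change in log10 "of Hypoxic Burden (HB) 4% plus one (scored in reference to AHI[4%]), 75/2.5 dose vs. placebo", and SAP 6.1 models that quantity. In SAP 6.1, untransformed HB is only a sensitivity analysis.

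**The concern.** Thirty participants is a small number for detecting 3.7 units against a within-subject SD of 9, even in a crossover, because the difference is only about 0.4 of that SD (3.7 / 9 = 0.41).

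This statement is the only quantitative justification of N in either document. A reader who accepts it will take a non-significant result at a true difference of 3.7 to carry a 20% false-negative risk. On the stated inputs that risk is about 65–72%. The 75/2.5 versus placebo test on HB also comes first in the testing order of SAP 4.5, so a miss there affects how the later tests are read.

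A second problem sits on top of the first. The SAP claims power on the primary endpoint using a difference and SD in %min/h, but the test it will run is on log10(HB + 1). The SAP therefore has no power statement for its own primary test.

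**Working it through.** **Inputs.** N = 30, two-sided alpha 0.05, difference d = 3.7 %min/h, SD = 9 and discontinuation below 20% (Protocol 8.1, SAP 9). No replacement (Protocol 4.1), so n = 30 × 0.8 = 24 completers at the limit. Three periods and six sequences, with every participant due to receive all three treatments (SAP 3.2.1).

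**Formulas.** With within-subject SD s, a participant's difference between two treatments has variance 2s², so SD(diff) = s√2 and SE = s√(2/n). Power was taken from the noncentral t distribution with noncentrality d/SE. The degrees of freedom were n − 1 (paired analysis) or 2n − 4 (three-period crossover model). A normal approximation is shown for comparison.

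**Literal reading: 9 is the within-subject SD.** SD(diff) = 9 × 1.414 = 12.73.

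| n | SE | d/SE | Power, paired t | Power, crossover t | Power, normal |
|---|---|---|---|---|---|
| 30 | 12.73/√30 = 2.32 | 1.59 | 33.7% | 34.6% | 35.7% |
| 24 | 12.73/√24 = 2.60 | 1.42 | 27.6% | 28.5% | 29.6% |

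80% power needs d/SE of at least 1.96 + 0.84 = 2.80. A simulation of the three-period crossover with 24 completers gave 28.4%.

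**Favourable reading: 9 is the SD of the paired difference.**

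| n | SE | d/SE | Power, paired t | Power, crossover t | Power, normal |
|---|---|---|---|---|---|
| 30 | 9/√30 = 1.64 | 2.25 | 58.6% | 60.0% | 61.5% |
| 24 | 9/√24 = 1.84 | 2.01 | 48.8% | 50.4% | 52.2% |

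**Other attempts to reproduce 80% with 24 to 30 participants.**

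- One-sided 0.05, contrary to the text: 40–48% with SD(diff) 12.73, and 62–73% with SD(diff) 9.
- Both active doses pooled against placebo: 44% (n = 30) or 36% (n = 24).
- 9 read as a variance: 98% or more, which overshoots.
- 9 read as the total SD per treatment, with correlation ρ: SD(diff)² = 2 × 81 × (1 − ρ). Reaching 80% needs SD(diff) of about 7.0–7.1 (n = 30) or 6.2–6.3 (n = 24). For example, 1 − 7.1²/162 = 0.69 and 1 − 6.2²/162 = 0.76, so ρ must be about 0.69–0.76. Neither document states a correlation, and both call the SD within-subject or within-participant.

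**What the inputs do support.**

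| Meaning of 9 | Detectable with 80% power, n = 30 | n = 24 | Completers needed for 80% at 3.7 |
|---|---|---|---|
| Within-subject SD | 6.6–6.7 %min/h | 7.4–7.6 %min/h | 93–95 |
| SD of paired difference | 4.7–4.8 %min/h | 5.3–5.4 %min/h | 47–49 |

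Working back from 80% power at 3.7, the within-subject SD would have to be about 4.9–5.0 (n = 30) or 4.4–4.5 (n = 24), roughly half the stated 9.

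**Does the planned model close the gap?** No. SAP 4.7 fits treatment and visit with no baseline covariate. SAP 4.6 uses one pre-randomisation baseline per participant, which cancels from the within-participant contrast. The extra degrees of freedom from the third period are already in the crossover-t columns.

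**Scale.** Power for log10(HB + 1) cannot be computed, because it needs a log-scale difference and SD and the documents give neither.

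**The case against.** The strongest reply is that 28% takes the term within-subject SD literally, and the term is often used loosely for the SD of within-participant differences. Neither document defines it. There is also a possible origin for the 80%: with SD(diff) = 9 and 48 paired differences, power is 79.7% (47 df) to 80.5% (92 df). Since 48 is two groups of 24, and 24 is 30 less 20%, a two-sequence calculation with 24 per sequence could have been used. This is conjecture and does not rescue the claim, because the trial would have about 24 completers in all, not 48. It does mean the right replacement figure may be nearer 50% than 28%, so the sponsor must say what 9 is before a new number is printed.

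Three further points stand as limits:

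- The 24-completer figures are a floor. The text says less than 20% discontinuation, and the mITT repeated-measures analysis can use partial data.
- The false-negative risk of 65–72% applies to untransformed HB. Power for the SAP's log-scale test could be higher or lower.
- The scale mismatch is with the SAP's endpoint only; the figure does match the protocol's untransformed endpoint.

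Neither document states a go/no-go rule, so the effect of a null result on dose decisions is a risk and not a stated consequence. None of this restores 80%.

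**Conclusion.** The concern holds. On the documents' own inputs, power to detect 3.7 %min/h at two-sided 0.05 is about 28% with 24 completers and 34–35% with 30, against the 80% stated. Under the more generous reading of 9 it is 49–60%. The ambiguity changes the size of the shortfall but does not remove it.

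The figures assume normally distributed within-participant differences, equal variance across treatments and no carryover. They describe untransformed HB only. For log10(HB + 1), the endpoint the SAP actually tests, the power is unknown.

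This must be fixed because the headline design claim is wrong as written in both documents and would pass into the study report. It does not make the trial invalid or require more participants.

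**What to change.** Restate Protocol 8.1 and SAP section 9 with N left at 30. First say what the 9 is and where it comes from, then give the figures that follow:

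- **Within-subject SD:** about 28% power at 3.7 %min/h with 24 completers, or 80% power for about 7.5 %min/h.
- **SD of the paired difference:** about 50% power at 3.7 with 24 completers, or 80% power for about 5.3–5.4 %min/h.
- **Total SD per treatment:** state the within-participant correlation used and its source. About 0.69–0.76 is needed to support 80%.

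Then add a power or detectable-effect statement for log10(HB + 1), giving the assumed within-participant SD and the assumed ratio on that scale. Label the %min/h statement as referring to untransformed HB.

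The cost is wording in two sections and a stated power or detectable difference that is less favourable, unless the third explanation is documented. No extra participants are needed, and conduct and analysis do not change.

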8.2 Populations for Analyses

For the purposes of analysis, the following analysis sets are defined:

Population	Description
Enrolled	All participants who signed the ICF (including screening failures).
Modified Intent to Treat (mITT) Population	The mITT Population comprises all participants who are randomized, take at least 1 dose of any of the study treatments, and have at least 1 measurement on the primary endpoint. Participants will be analyzed for efficacy according to the treatment group into which they are randomized.
Safety Population	The Safety Population consists of all participants who are randomized and receive at least 1 dose of any of the study treatments. Participants will be analyzed for safety based on the treatment received. A precise definition of "as actually received" will be added in the Statistical Analysis Plan (SAP).
Per Protocol (PP) Population	The PP Population consists of all participants without any major protocol violations that could influence efficacy assessment. Participants in this population will be analyzed according to the treatment they actually received.

8.3 Interim Analyses

No interim analysis is planned.

9 Supporting Documentation and Operational Considerations

9.1 Appendix 1: Regulatory, Ethical, and Study Oversight Considerations

9.1.1 Regulatory and Ethical Considerations

- This study will be conducted in accordance with the protocol and with:
 - Consensus ethical principles derived from international guidelines including the Declaration of Helsinki and Council for International Organizations of Medical Sciences International Ethical Guidelines.
 - Applicable International Conference on Harmonisation (ICH) Good Clinical Practice (GCP) Guidelines.
 - Applicable laws and regulations.

- The protocol, protocol amendments, ICF, Investigator's Brochure, and other relevant documents (e.g., advertisements) must be submitted to an IRB/IEC by the Investigator and reviewed and approved by the IRB/IEC before the study is initiated.
- Any amendments to the protocol will require IEC/IRB approval before implementation of changes made to the study design, except for changes necessary to eliminate an immediate hazard to study participants.
- The Investigator will be responsible for the following:
 - Providing written summaries of the status of the study to the IRB/IEC annually or more frequently in accordance with the requirements, policies, and procedures established by the IRB/IEC.
 - Notifying the IRB/IEC of SAE or other significant safety findings as required by IRB/IEC procedures.
 - Overall conduct of the study at the site and adherence to requirements of 21 Code of Federal Regulations (CFR), ICH GCP guidelines, the IRB/IEC guidelines, European regulation 536/2014 for clinical studies (if applicable), and all other applicable local regulations.

9.1.2 Financial Disclosure

Investigators and sub-Investigators will provide the Sponsor with sufficient, accurate financial information in accordance with local regulations to allow the Sponsor to submit complete and accurate financial certification or disclosure statements to the appropriate regulatory authorities. Investigators are responsible for providing information on financial interests during the course of the study and for 1 year after completion of the study.

9.1.3 Informed Consent Process

- The Investigator or his/her representative will explain the nature of the study to the participant or his/her legally authorized representative and answer all questions regarding the study.
- Participants must be informed that their participation is voluntary. Participants will be
 required to sign a statement of informed consent that meets the requirements of 21 CFR 50,
 local regulations, ICH guidelines, Health Insurance Portability and Accountability Act
 requirements, where applicable, and the IRB/IEC or study center.

- The medical record must include a statement that written informed consent was obtained before the participant was enrolled in the study and the date the written consent was obtained. The authorized person obtaining the informed consent must also sign the ICF.
- Participants must be re-consented to the most current version of the ICF(s) during their participation in the study.
- A copy of the signed ICF(s) must be provided to the participant or the participant's legally authorized representative.

If a protocol amendment is required, the ICF may need to be revised to reflect the changes to the protocol. If the ICF is revised, it must be reviewed and approved by the appropriate IEC/IRB, and signed by all participants subsequently enrolled in the study as well as those currently enrolled in the study.

9.1.4 Data Protection

- Participants will be assigned a unique identifier by the Sponsor. Any participant records or
 datasets that are transferred to the Sponsor will contain the identifier only; participant names
 or any information which would make the participant identifiable will not be transferred.
- The participant must be informed that his/her personal study-related data will be used by the Sponsor in accordance with local data protection law. The level of disclosure must also be explained to the participant.
- The participant must be informed that his/her medical records may be examined by Clinical Quality Assurance auditors or other authorized personnel appointed by the Sponsor, by appropriate IRB/IEC members, and by inspectors from regulatory authorities.

9.1.5 Data Quality Assurance

- All participant data relating to the study will be recorded on printed or eCRFs unless transmitted to the Sponsor or designee electronically (e.g., laboratory data). The Investigator is responsible for verifying that data entries are accurate and correct by physically or electronically signing the eCRF.
- The Investigator must maintain accurate documentation (source data) that supports the information entered in the eCRF.
- The Investigator must permit study-related monitoring, audits, IRB/IEC review, and regulatory agency inspections and provide direct access to source data documents.

- The Sponsor or designee is responsible for the data management of this study including quality checking of the data.
- Study monitors will perform ongoing source data verification to confirm that data entered into the eCRF by authorized site personnel are accurate, complete, and verifiable from source documents; that the safety and rights of participants are being protected; and that the study is being conducted in accordance with the currently approved protocol and any other study agreements, ICH GCP, and all applicable regulatory requirements.
- Records and documents, including signed ICF, pertaining to the conduct of this study must be
 retained by the Investigator for 5 years after study completion unless local regulations or
 institutional policies require a longer retention period. No records may be destroyed during
 the retention period without the written approval of the Sponsor. No records may be
 transferred to another location or party without written notification to the Sponsor.
- All data generated by the site personnel will be captured electronically at each study center using eCRFs. Data from external sources (such as laboratory data) will be imported into the database. Once the eCRF clinical data have been submitted to the central server at the independent data center, corrections to the data fields will be captured in an audit trail. The reason for change, the name of the person who performed the change, together with the time and date will be logged to provide an audit trail.
- If additional corrections are needed, the responsible monitor or data manager will raise a query in the electronic data capture (EDC) application. The appropriate staff at the study site will answer queries sent to the Investigator. The name of the staff member responding to the query, and time and date stamp will be captured to provide an audit trail. Once all source data verification is complete and all queries are closed, the monitor will lock the database.
- The specific procedures to be used for data entry and query resolution using the EDC system/eCRF will be provided to study sites in a training manual. In addition, site personnel will receive training on the EDC system/eCRF.

9.1.6 Source Documents

- Source documents provide evidence for the existence of the participant and substantiate the integrity of the data collected. Source documents are filed at the Investigator's site.
- Data entered in the eCRF that are transcribed from source documents must be consistent with the source documents or the discrepancies must be explained. The Investigator may need to request previous medical records or transfer records, depending on the study. Also, current medical records must be available.

9.1.7 Study and Site Closure

The Sponsor designee reserves the right to close the study site or terminate the study at any time for any reason at the sole discretion of the Sponsor. Study sites will be closed upon study completion. A study site is considered closed when all required documents and study supplies have been collected and a study site closure visit has been performed.

The Investigator may initiate study site closure at any time, provided there is reasonable cause and sufficient notice is given in advance of the intended termination.

Reasons for the early closure of a study site by the Sponsor or Investigator may include but are not limited to:

- Failure of the Investigator to comply with the protocol, the requirements of the IRB/IEC or local health authorities, the Sponsor's procedures, or GCP guidelines.
- Inadequate recruitment of participants by the Investigator.
- Discontinuation of further study treatment development.

9.1.8 Publication Policy

- The Sponsor will generally support publication of multicenter studies only in their entirety and not as individual site data.
- Authorship will be determined by mutual agreement and in line with International Committee of Medical Journal Editors authorship requirements.
- The Sponsor retains the right to disapprove any submission for publication, including any publication using trial data, including abstracts, presentations or manuscripts.
- A summary of the study results will also be posted in a publicly accessible database (e.g., www.ClinTrials.gov).

9.1.9 Protocol Approval and Amendment

Before the start of the study, the study protocol and/or other relevant documents will be approved by the IEC/IRB/Competent Authorities, in accordance with local legal requirements. The Sponsor must ensure that all ethical and legal requirements have been met before the first participant is enrolled in the study.

This protocol is to be followed exactly. To alter the protocol, amendments must be written, receive approval from the appropriate personnel, and receive IRB/IEC/Competent Authority approval prior to implementation (if appropriate). Following approval, the protocol amendment(s) will be submitted to the US Investigational New Drug (IND) under which the study is being conducted.

Administrative changes (not affecting the participant benefit/risk ratio) may be made without the need for a formal amendment. All amendments will be distributed to all protocol recipients, with appropriate instructions.

9.1.10 Liability and Insurance

The Sponsor will take out reasonable third-party liability insurance cover in accordance with all local legal requirements. The civil liability of the Investigator, the persons instructed by him or her and the hospital, practice, or institute in which they are employed and the liability of the Sponsor with respect to financial loss due to personal injury and other damage that may arise as a result of the carrying out of this study are governed by the applicable law.

The Sponsor will arrange for participants participating in this study to be insured against financial loss due to personal injury caused by the pharmaceutical products being tested or by medical steps taken in the course of the study.

9.1.10.1 Access to Source Data

During the study, a monitor will make site visits to review protocol compliance, compare EDC/eCRF entries and individual participant's medical records, assess drug accountability, and ensure that the study is being conducted according to pertinent regulatory requirements. The EDC/eCRF entries will be verified with source documentation. The review of medical records will be performed in a manner to ensure that participant confidentiality is maintained.

Checking of the EDC/eCRF entries for completeness and clarity, and cross-checking with source documents, will be required to monitor the progress of the study. Moreover, regulatory authorities of certain countries, IRBs, IECs, and/or the Sponsor's Clinical Quality Assurance Group may wish to carry out such source data checks and/or on-site audit inspections. Direct access to source data will be required for these inspections and audits; they will be carried out giving due consideration to data protection and medical confidentiality. The Investigator assures the CRO and the Sponsor of the necessary support at all times.

